Data will be entered into a secure and validated database using eCRFs. Data entered may be checked at the point of entry and through external validation checks for accuracy. After resolution of any discrepancies and automated data-review procedures, the final data sets will be subject to a quality assurance audit. When the database is declared to be complete and accurate, it will be locked. Any changes to the database after that time can only be made by written notice. The investigator will be responsible for ensuring the accuracy, completeness, and timeliness of the data reported to the sponsor in the CRFs and in all required reports. Data reported on the CRFs, which are derived from source documents, should be consistent with source documents or the discrepancies should be explained. To ensure the quality of the clinical data across all participants and sites, a clinical data management review will be performed on all patient data. During this review, patient data will be checked for consistency, omissions, and any apparent discrepancies. In addition, the data will be reviewed for adherence to protocol and GCPs. To resolve any questions arising from the clinical data-review process, data queries will be sent for the site to complete. The principal investigator will electronically sign and date the indicated places on the CRF. This signature will indicate that the principal investigator inspected or reviewed the data on the CRF and the data queries, and that the investigator agreed with the content.

i.) Study Files and Retention of Records

- 1. The investigator must maintain adequate and accurate records to fully document the conduct of the study and to ensure that study data is subsequently verified. These documents should be classified into two separate categories: (1) investigator's study file, and (2) patient clinical source documents. The investigator's study file will contain the protocol/amendments, printed (or electronically archived) copies of the patient CRFs, IRB, and governmental approval with correspondence, informed consent, drug accountability (receipt/dispensing) records, staff curriculum vitae and authorization forms, information regarding monitoring activities, investigator correspondence, and other appropriate documents and correspondence.
- 2. Patient clinical source documents for this study would include, but are not limited to, the following:
 - a. Patient identification (name, date of birth, gender)
 - b. Documentation that patient meets eligibility criteria, i.e., relevant medical history, physical examination, and confirmation of diagnosis
 - c. Dated notes of the day of entry into the study including study number, patient identification number, verification that the trial was discussed and written informed consent was obtained
 - d. Dated notes for each protocol assessment and documentation that protocol specific procedures were performed
 - e. Documentation of all adverse events, including any action taken with regard to study intervention and outcome

- f. Concomitant medications (including start and end date, dose if relevant)
- g. Date of trial completion and reason for early discontinuation, if applicable

j). Confidentiality

The investigator must ensure that all participants' confidentiality will be strictly maintained and that their identities are protected from unauthorized parties. Only patient initials, date of birth, and an identification code (i.e., not names) should be recorded on any form or biological sample submitted to the sponsor, IRB, or laboratory. The investigator must keep a screening log showing codes, names and addresses for all patients screened and for all patients enrolled in the trial. On CRFs or other documents that are submitted to the sponsor, participants should be identified by an identification code and not by their names.

k.) Protocol and Protocol Amendments

- 1. The investigator is responsible for ensuring the study is conducted in accordance with the procedures and evaluations described in this protocol. No amendments will be permitted to this protocol or to the conduct of the study without approval from the IRB. These communications will be documented in writing.
- 2. All protocol amendments must be submitted to the IRB in accordance with local requirements. Approval must be obtained before changes are implemented.

XI. References

- 1. Chey, W. D., Kurlander, J., & Eswaran, S. (2015). Irritable Bowel Syndrome: A Clinical Review. *JAMA*, *313*(9), 949. https://doi.org/10.1001/jama.2015.0954
- 2. Lovell, R. M., & Ford, A. C. (2012). Global Prevalence of and Risk Factors for Irritable Bowel Syndrome: A Meta-analysis. Clinical Gastroenterology and Hepatology, 10(7), 712-721.e4. https://doi.org/10.1016/j.cgh.2012.02.029

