Pilot Study Investigating the Effect of Tai Chi as Treatment for IBS-C

NCT: NCT04132804

Principal/Overall Investigator: [name], MPH

Funding: None

Version Date: September 22, 2020

I. Background and Significance

a.) Historical background

Irritable bowel syndrome (IBS) is a functional gastrointestinal disorder (FGID) characterized by abdominal pain and altered bowel habits. IBS is chronic and relapsing, causing significant reductions in health-related quality of life and work productivity. As the most commonly diagnosed gastrointestinal disorder, IBS affects between 4%-22% of the general population worldwide.² In the United States, the distribution is approximately equal among IBS with constipation (IBS-C), IBS with diarrhea (IBS-D), and IBS with a mixed bowel pattern (IBS-M). IBS is diagnosed in the absence of other medical causes with a pathogenesis mainly focused on abnormalities in gastrointestinal motility, visceral sensation, brain-gut interaction, and psychosocial distress. Therefore, treatment options for IBS are aimed at various action sites of the brain-gut axis through the use of pharmacotherapy and dietary/lifestyle changes. In the case of IBS-C, strong methodological evidence for various types of conventional pharmacotherapy, such as bulking agents, prokinetics, and antispasmodics, is lacking. With inadequate relief from IBS symptoms, many patients seek out complementary and alternative medicine (CAM) therapies which are medical practices that are not considered to be a part of conventional medicine.⁵ A subset of CAM therapies focuses on mind-body interventions. 6 In recognition of the communication between brain and gut, one such mind-body practice that may be beneficial for patients with IBS-C is the ancient practice of Tai Chi.

Tai Chi Chuan (taijiquan) or Tai Chi is a mind-body practice borne of Chinese philosophy and martial arts which has been practiced for centuries to promote deep relaxation, strengthened health, and to prevent injuries and illness. The principle behind the practice is that Tai Chi improves the circulation of blood and Qi (energy) throughout the body which enhances the body's natural healing capabilities. Tai Chi achieves this through gentle moving meditation and focusing on five building blocks: body, breath, mind, energy, and spirit. Through this method, Tai Chi practitioners exercise a balance between strength and flexibility, condition muscles, increase bone density, and massage their internal organs.⁷

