Through reinforcement of the mind-body connection, Tai Chi may be helpful in relieving chronic abdominal pain associated with IBS-C. The gentle moving meditation involved in Tai Chi practice may influence proper breathing and abdominal wall control in addition to massaging internal organs through movement.

Previous research has suggested that therapies engaging the mind-body connection may have promising effects on functional bowel disorders in general, and on IBS specifically. ^{18, 5} Some mind-body therapies, such as gut-focused hypnotherapy, have already gained approval as an effective treatment in reducing symptoms of IBS. ¹⁹ Similarly to already established mind-body therapies, Tai Chi may positively impact symptoms of IBS-C by changing sensory perception or even calming colonic motility. Tai Chi practice could lead to reduced abdominal distention and improved anxiety and depression scores.

II. Specific Aims

This is a single center pilot study. The purpose of the study is to evaluate the efficacy of Tai Chi practice in reducing symptoms of IBS. Patients who meet the Rome IV criteria for IBS-C and who meet the inclusion criteria will be offered participation in the study. We hypothesize that patients practicing Tai Chi will have reduced symptoms of IBS-C as measured through the Global Assessment of Relief, Irritable Bowel Syndrome Severity Scoring System (IBS-SSS), Irritable Bowel Syndrome Quality of Life (IBS-QOL), Visual Analogue Pain Scale, and abdominal distention. We also hypothesize that daily entries made through the GeoPain app will show a trend toward reduced pain intensity.

III. Subject Selection

This study aims to recruit 24 total subjects to be enrolled at one site, Massachusetts General Hospital. The 24 subjects that this study aims to recruit factors in a dropout rate of 15%, with a final sample size of 20 subjects.

INCLUSION/EXCLUSION CRITERIA:

Inclusion

- 1. Age 18 70 years
- 2. BMI \leq 35
- 3. Rome IV criteria for IBS-C
- 4. Continued IBS-C throughout run-in period
- 5. Compliant with reporting during run-in
- 6. Ability to follow verbal and written instructions
- 7. Ability to record daily patient reported outcomes via RedCap survey
- 8. Ability to use the GeoPain app on a smart phone
- 9. Ability to use Zoom as a platform for conducting study visits virtually
- 10. Ability to respond to 80% of the daily diaries
- 11. Ability to attend at least 7 out of 8 Tai Chi classes
- 12. Informed consent form signed by the subjects

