1. Patients agreeing to participate will sign an informed consent with the study physician or research coordinator at the time of enrollment, after proper informed consent has been provided by the site. Due to COVID-19 restrictions and social distancing, REDCap eConsent will take the place of written documentation of informed consent.

c.) Treatment Assignment

1. All patients will participate in 8 weeks of one-hour Tai Chi sessions once per week.

V. Study Procedures

a) Remote conduct of study visits and procedures

Due to COVID-19 and its restrictions, all eligibility screening and study visits listed below will be performed remotely until restrictions are lifted at the study site. All remote visits will be conducted over Zoom and the visit schedule will not change. All research staff will follow the MGH requirements for using Zoom (Enterprise Zoom as well as Healthcare Zoom- for any study visits involving patient care.) All questionnaires will be administered remotely via REDCap or over the phone. All Zoom link invites will be password protected and emailed by research staff to study participants using Send Secure or unencrypted email, depending on the subject's preference.

b.) Study visits and parameters to be measured

- 1. Eligibility Screen (to be conducted via Healthcare Zoom)
 - a. Obtain informed consent (performed by research staff)
 - b. Collect demographic data (performed by research staff)
 - c. Assessment of sufficient space to perform Tai Chi in-home (performed by research staff)
 - d. Assess inclusion/exclusion criteria (performed by research staff)
 - e. Rome IV questionnaire to screen for IBS-C (performed by research staff)
 - f. Collect medical and surgical history (performed by research staff)
 - g. Collect concomitant medications (performed by research staff)
 - h. Self report of height, weight, and waist measurement (if restrictions are lifted and study visits are being performed on site, vital signs will be recorded) (performed by research staff)
 - i. Perform brief physical examination by study physician
 - j. Visual Analogue Pain Scale (performed by research staff)
 - k. Questionnaires including Global Assessment of Relief, Hospital Anxiety and Depression Scale (HADS), Gastrointestinal Symptom Rating Scale-IBS version (GSRS-IBS), Irritable Bowel Syndrome-Behavioral Responses Questionnaire (IBS-BRQ), Fear of Food Questionnaire (FFQ), Visceral Sensitivity Index (VSI), IBS-SSS, and IBS-QOL(performed by research staff)

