One day prior to the treatment period, subjects will again complete the Rome IV questionnaire confirming that inclusion and exclusion criteria continue to be satisfied.

Subjects will be asked to refrain from making any major lifestyle changes (e.g. starting a new diet or changing their exercise pattern outside of Tai Chi practice) during the study.

During the treatment period, subjects will meet via Zoom once per week for one-hour Tai Chi lessons with an experienced instructor. A member of the research staff will send the password-protected Zoom invitation link to the subject's preferred email address via Send Secure or regular email, depending on the subject's preference. Subjects will also be instructed to practice Tai Chi at home outside of the lessons using the instructions, handouts, and guidance from the instructor.

Subjects will be instructed to complete a daily REDCap diary entry and a daily GeoPain entry to record information about stool frequency and consistency, abdominal bloating, abdominal discomfort, and abdominal pain. Subjects will also use the REDCap diary to report rescue medication use and daily Tai Chi practice.

The lessons will occur on Days 0, 7, 14, 21, 28, 35, 42, and 49. The Tai Chi lessons will take place remotely via Zoom. Should restrictions be lifted and study visits be performed on site, lessons will take place in the Simches Research Center at [name].

On Days 0, 21, and 49 subjects will be phoned by a member of the research staff for

assessments prior to their regularly scheduled Tai Chi lesson. Assessments will include vitals (if the study is operating on site only), weight, height, waist circumference, leg strength, and questionnaires. Assessments will be completed with research staff over the phone or, if restrictions are lifted and study visits are conducted on site, at the Center for Neurointestinal Healthcare at [name], after which subjects will go to their regularly scheduled Tai Chi lesson at Simches. Participants will also complete a qualitative survey over the phone with a member of the study staff that will be audio recorded and later transcribed in order to gain a full, complete, qualitative understanding of the patient's perspective of the investigational treatment that was used.

4. Post-Treatment Period (Day 77)

Subjects will complete a REDCap diary entry regarding symptoms 28 days post-treatment, 4 weeks after the final study visit.

5. Schedule of Events

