Study Procedures	Screening	Run-In (Up	Treatment								Post- Treatment
Visit	Visit 1 (Up to 3 months prior to treatment)	to 3 months prior to Treatment)	Visit 2 (Day 0)	Visit 3 (Day 7)	Visit 4 (Day 14)	Visit 5 (Day 21)	Visit 6 (Day 28)	Visit 7 (Day 35)	Visit 8 (Day 42)	Visit 9 (Day 49)	4 Weeks Post- Treatment (Day 77)
Informed Consent	Х										
Inclusion/exclusion criteria	х										
Demographics, medical history, and medication history	Х										
Concurrent medical conditions and concomitant medications	х		х			х				х	х
Physical examination	X										
Vital signs	Х		Х			Х				Х	Х
Weight, height, waist circumference (a)	x		Х			Х				Х	×
Pregnancy test	Х										
Tai Chi Lessons			Х	Х	Х	Х	Х	Х	Х	Х	
Stool Sample	Х									Х	Х
Daily Diary		Х	Х	Х	Х	Х	Х	Х	Х	Х	Х
GeoPain Reporting		Х	Х	Х	Х	Х	Х	Х	Х	Х	Х
Global Assessment of Relief	х		х	х	х	х	х	х	Х	Х	Х
HADS	Х		Х			Х				Х	Х
VSI	Х		Х			Х				Х	Х
Visual Analogue Pain Scale	х		Х	Х	Х	х	х	х	Х	Х	Х

Rome IV Questionnaire	Χ							
IBS-SSS	Χ		Х		Х		Χ	Х
IBS-QOL	Х		Х		Х		Χ	Х
GSRS-IBS	Х		Х				Χ	Х
IBS-BRQ	Х		Х				Χ	Х
Fear of Food Questionnaire	Х		Х				Х	Х
Leg strength Assessment	Х		Х		Х		Х	Х
Treatment Satisfaction							Х	Х
Pre-treatment AE Assessment	Х	Х						
AE Assessment	Χ		Х		Х		Χ	Χ
Qualitative Post-Tx Survey							Х	
CSQ							Х	
Instructor Assessment							Х	Х

⁽a) Weight, height, and waist circumference are measured and BMI is calculated at initial screening visit only. Weight and waist circumference only is measured at subsequent visits.

6. Investigational Treatment to be Used

Subjects will practice Tai Chi via Zoom (if on site, at the Simches Research Center.) We will use a standardized Tai Chi protocol derived from previously tested trials ^{10,11,12,13}. The Tai Chi program will be based upon the classical Yang Tai Chi philosophy which includes 108 postures show to be a moderate intensity exercise.

In the first session, the Tai Chi instructor will explain the program, exercise theory, and procedures of Tai Chi. The patients will be provided with printed materials on the Tai Chi Mind-Body program including Tai Chi principles, practicing techniques, and safety precautions. Subjects will then begin Tai Chi practice under the instruction of the Tai Chi instructor. The Tai Chi instructor will have extensive experience (>20 years) conducting Tai Chi mind-body programs and will be following a Tai Chi protocol specifically designed for individuals with IBS-C.

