 Stool will be stored to check for metabalomics that may profile changes between the pre-treatment and treatment sample.
- 2. Microbiome Analysis
 Standard 16s rRNA sequencing for taxonomic identification and metagenomic profiling of the gut microbiome will be performed on stool samples to profile microbiome diversity and changes in microbiome between the pre-treatment and treatment sample.

VII. Biostatistical Analysis

- a.) Endpoint analyses
 - 1. Primary endpoint: IBS-SSS will be compared in a paired fashion for individual patients before and after the intervention using repeated measures t-test.
 - 2. Secondary endpoints: The secondary endpoints (as outlined in section V.a.6.b.) will be compared in a similar fashion.

b.) Power analysis

This is a single-center clinical exploratory pilot investigating the treatment of IBS-C using Tai Chi. As a pilot study, we hope to enroll 24 subjects with a final sample size of 20 subjects. The study will be conducted in two cycles of at least 10 subjects each to facilitate a full classroom size. Based on a previous pilot study involving Tai Chi as treatment for rheumatoid arthritis¹², 20 subjects appears to be a feasible number for detecting a trend toward outcomes that can be investigated in a future larger clinical trial.

VIII. Risks and Discomforts

a.) Tai Chi

Tai Chi is a relatively safe practice that is unlikely to cause injury if done with proper instruction. Caution should be exercised with conditions such as pregnancy, hernia, joint problems, and severe osteoporosis.

b.) Other Possible Risks

Other possible risks and side effects include skin irritation from inadvertently coming in contact with preservatives in the specimen collection materials, breach of confidentiality involving protected health information, and that information about taking part in a metabolic/microbiome study could influence insurance companies or employers regarding the patient's health. Study IDs will be utilized to minimize breaches of confidentiality. Filling out questionnaires could cause patients to feel uncomfortable.

IX. Potential Benefits

- a.) It is hypothesized that Tai Chi may be of benefit in patients with IBS-C. Potential benefits may include a decrease in self-reported abdominal pain/discomfort, straining, bloating, and constipation severity, as well as improved quality of life and symptoms severity.

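### The stated aim is efficacy, but a single-arm before/after t-test of IBS-SSS cannot separate Tai Chi from change that would have happened anyway

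*Combined protocol and SAP*

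**What the plan says.** Section II (Specific Aims) gives the purpose: "The purpose of the study is to evaluate the efficacy of Tai Chi practice in reducing symptoms of IBS". Its hypothesis is that patients practising Tai Chi will have fewer symptoms on several measures, IBS-SSS among them.

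Section IV.c describes a single arm: "All patients will participate in 8 weeks of one-hour Tai Chi sessions once per week".

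Section VII.a gives the primary analysis: "IBS-SSS will be compared in a paired fashion for individual patients before and after the intervention using repeated measures t-test". The secondary endpoints "will be compared in a similar fashion".

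Section VII.b is more modest. It calls the study an exploratory pilot and justifies 20 subjects as feasible for "detecting a trend toward outcomes that can be investigated in a future larger clinical trial".

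The Schedule of Events places IBS-SSS at Screening (up to 3 months before treatment), Day 0, Day 21, Day 49 and Day 77. Section V, item 3 puts the Day 0 assessments before the first lesson.

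**The concern.** The paired t-test has the null hypothesis of no mean change in IBS-SSS. An efficacy aim needs a test against the null of no Tai Chi effect. The two coincide only if untreated patients would not change on average, and the plan offers nothing to support that. Section I.a says "IBS is chronic and relapsing", and entry requires active IBS-C that continues through run-in. Natural course, regression to the mean, expectation and attention from staff therefore all enter the same mean change as any effect of Tai Chi.

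Under an efficacy aim, a significant result would be read as showing that Tai Chi works. The pilot is meant to lead to a larger trial, and within-person change mistaken for a treatment effect could distort that trial's planning.

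**Working it through.** **Sample size, the plan's one reproducible figure.** 20 completers with 15% dropout: 20 / (1 − 0.15) = 23.5, rounded up to 24, as Section III states. The 20 itself cannot be derived, because no alpha, power, effect size or SD is given.

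**Does any planned analysis supply a comparison for IBS-SSS?**
- Allocation (IV.c): all participants receive Tai Chi.
- Primary and secondary analyses (VII.a): before/after only.
- Historical benchmark or performance goal: none in the document.
- Untreated IBS-SSS data: only the Screening and Day 0 values. The run-in diary and GeoPain entries record other measures. The plan does not say that the Screening to Day 0 change will be reported.

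**How often would the test be significant if Tai Chi did nothing?** Inputs: n = 20 (Sections III and VII.b); two-sided alpha 0.05 (assumed); untreated improvement of d SDs of the change score (assumed, since the documents give no value). The critical value is t(0.975, 19) = 2.093. The probability of a significant improvement is P(T > 2.093), where T is noncentral t with 19 df and noncentrality d√20.

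| Untreated change d | d√20 | Significant improvement, n = 20 | If all 24 complete |
|---|---|---|---|
| −0.2 (worsening) | −0.89 | 0.25% | – |
| −0.1 (worsening) | −0.45 | 0.85% | – |
| 0 | 0 | 2.50% | 2.50% |
| 0.1 | 0.45 | 6.24% | 6.81% |
| 0.2 | 0.89 | 13.35% | 15.37% |
| 0.3 | 1.34 | 24.65% | 29.07% |
| 0.5 | 2.24 | 56.45% | 65.04% |

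Simulating 400,000 trials gave the n = 20 figures to within 0.1 percentage points. The worsening rows show the opposite error: untreated deterioration would hide a real benefit.

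**What could the Screening to Day 0 change show?** Its 95% CI half-width at n = 20 is 2.093 / √20 = 2.093 / 4.472 = 0.468 SD of that change. The CI would include zero with probability 100 − 13.35 − 0.25 = 86.4% if the true drift were an improvement of 0.2 SD, and 100 − 56.45 = about 44% at 0.5 SD. It can flag only large drift.

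**The case against.** The strongest reply is that this is a pilot and says so in its title, in Section II directly before the purpose sentence, and in Section VII.b. The working hypothesis is only that symptoms will fall, and a paired test is the right test of that. This tempers the point, and a single-arm pilot is a legitimate design. It does not remove the mismatch: the efficacy purpose is current text in the aims section, and nothing in the document limits causal interpretation.

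The plan also restricts some other causes of change. Permitted medications must be at stable doses, new mind-body practices are excluded, major lifestyle changes are discouraged, and rescue use is recorded. These are real safeguards, but they do not deal with natural fluctuation, regression to the mean or expectation. Daily run-in data give an untreated reference period for several secondary outcomes, but it is two weeks long and does not cover IBS-SSS.

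Three further objections stand. The drift sizes are assumed, so the percentages illustrate the problem and do not measure it in this trial. The plan does not say that the observed change will serve as an effect size for the larger trial, so that harm is inferred. The Screening to Day 0 estimate is weak and should rank below the change of wording.

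**Conclusion.** The concern holds. As written, the plan would support an efficacy conclusion that its design cannot deliver. This follows from the single arm and the before/after test, and does not depend on any assumed drift.

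The possible size can only be illustrated. With 20 completers, an assumed two-sided alpha of 0.05 and no Tai Chi effect, untreated improvement of 0.1 to 0.5 SD of the change score gives a significant improvement in 6% to 56% of trials, against 2.5% with no drift. Worsening of 0.1 to 0.2 SD lowers this to 0.9% to 0.3%. Neither the size nor the direction of the real drift can be known from the documents: there is no IBS-SSS entry threshold, and patients with the worst pain score are excluded.

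The study remains worth running. The stated purpose and the planned conclusion should be corrected.

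**What to change.** 1. **Main change.** Reword the purpose in Section II along these lines: *to estimate within-participant change in IBS-SSS over the Tai Chi programme, to inform a controlled trial.* In Section VII.a, plan to report the mean Day 0 to Day 49 change with its 95% CI, and state that without a control group it cannot be attributed to Tai Chi. This is sufficient on its own.

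2. **Secondary.** Report the Screening to Day 0 IBS-SSS change descriptively, with its 95% CI and the interval length, beside the Day 0 to Day 49 change. Do not subtract one from the other. State its limits: the interval varies, participants keep diaries during run-in, and those whose IBS-C does not continue are removed (the day before treatment, "subjects will again complete the Rome IV questionnaire confirming that inclusion and exclusion criteria continue to be satisfied"). State also that a CI including zero does not show absence of drift.

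3. **Minor clarification.** Name Day 0 and Day 49 as the before and after visits in Section VII.a. They are the natural reading, but Section V, item 7.b.8 lists a pre-treatment value separately from study visit 2 for other questionnaires.

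The cost is wording in two sections and one estimate from data already scheduled, with no new visits or participants. The price is a more modest claim and an imprecise extra estimate. Splitting the same 20 subjects into 10 treated and 10 controls is not proposed: the 95% CI half-width for the difference would be 2.101 × √(2/10) = 0.94 SD, twice that of the single-arm change.
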